9.3.1. Exposure

The date of the first dispensing of ritlecitinib during the study period will be the index date. The exposure will continue until the end of a 90-day grace period following the estimated discontinuation of the index treatment. Duration of each dispensing will be computed based on days supplied, estimated based on assumed daily dose, package size, and number of packages in each dispensing. Only the first continuous treatment episode will be considered in this study.

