8.2. Study Objectives

The study objectives are to:

- 1. Evaluate, to the extent measurable in the available routinely collected data, indicators of HCP's adherence to the risk minimization measures (RMMs) in accordance with the ritlecitinib SmPC, HCP guide, and Patient Card, specifically:
 - Performing laboratory tests of lymphocyte count, platelet count, hepatitis B/C, and tuberculosis (TB) screening prior to initiation of ritlecitinib treatment
 - Performing laboratory tests of lymphocyte count and platelet count at week 4 (± 2 weeks) from initiation of ritlecitinib treatment
 - Avoiding live attenuated vaccines shortly before and during treatment with ritlecitinib
 - No use during pregnancy
 - No use in patients aged < 12 years
 - No use during serious infections
- 2. Describe the characteristics of patients before initiation of ritlecitinib treatment, in terms of:
 - Risk factors for thromboembolic events (including deep vein thrombosis (DVT), pulmonary embolism (PE), and arterial thrombosis)
 - Risk factors for malignancy
 - Risk factors for cardiovascular disease (CVD)

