9.5. Study Size

This is a descriptive study, and no comparative analyses will be conducted. Thus, the purpose of the sample size calculations provided below is to describe the expected precision of the estimates.

The following formula, based on the normal approximation to the binomial proportion, was used to calculate the sample size for this study:

$$n = \frac{P \cdot (1 - P) \cdot \left(Z_{1 - \alpha/2}\right)^2}{e^2},$$

Where P is the expected proportion of patients with evidence of having performed the recommended RMMs prior to/during treatment with ritlecitinib; e is the margin of error, or half the desired width of the CI; and $Z_{1-\alpha/2}$ is the standard normal Z-score corresponding to a cumulative probability of $1-\alpha/2$.

The proportion of patients with evidence of having performed the recommended RMMs prior to/during treatment with ritlecitinib (*p*) is not known in advance. Assuming varying proportions, the associated sample size and specified margins of error are provided in Table 2.

Table 2. Required Number of Ritlecitinib Treated Patients by Proportion of Patients With Evidence of Having Performed the Recommended Risk Minimization Measures (RMMs) and 95% Confidence Interval (CI) Width

Proportion of patients with evidence of having performed the recommended RMMs	Width of 95% CI (%)	Required number of patients
25%	10.0	289
	15.0	129
	20.0	73
50%	10.0	385
	15.0	171
	20.0	97
75%	10.0	289
	15.0	129
	20.0	73

Abbreviations: CI = confidence interval; RMM(s) = risk minimization measure(s).

The proportion of 50% yields the most conservative (i.e., the largest) sample size for a specified margin of error. In Table 2, a *minimum* sample size of 385 patients per database would maximize the precision of estimates. With 385 patients, the width of the CI will decrease as the proportion of patients with evidence of having performed the recommended RMMs approaches the extremes (0% and 100%, Table 3).

Table 3. Width of 95% Confidence Interval for a Range of Proportions, Assuming 385 Enrolled Patients

Proportion of patients with evidence of having	Width of
performed the recommended RMMs	95% CI (%)
10%	6.0
20%	8.0
30%	9.2
40%	9.8
50%	10.0
60%	9.8
70%	9.1
80%	8.0
90%	6.0

Abbreviations: CI = confidence interval; RMM(s) = risk minimization measure(s).

The study will include all patients identified during the study period who meet the eligibility criteria to maximize the precision of the estimates.

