9.7. Data Analysis

This is a descriptive study and the data will be analysed and results presented separately by country. Counts and proportions for categorical variables and mean and median with ranges for continuous variables will be calculated to address the study objectives, as below. All proportions will be reported with 95% CIs.

Data sources vary in collection of laboratory test and vaccine information (data on both laboratory tests and their results are available in Denmark; data on performed laboratory tests, but not results, are available in France; laboratory data are not available in Sweden). Data on vaccines are not available in Sweden.

Counts and proportions will be calculated for:

- 1. Patients with evidence of having performed the following laboratory tests and screenings within 3 months before index date:
 - Lymphocyte count
 - Platelet count
 - Screening for TB
 - Screening for viral hepatitis B and C
- 2. Patients with evidence of having performed the following laboratory tests at week 4 (\pm 2 weeks) after index date:
 - Lymphocyte count
 - Platelet count

- 3. Patients with evidence of having received live attenuated vaccines within 4 weeks before index date
- 4. Patients with evidence of having received live attenuated vaccines during treatment with ritlecitinib
- 5. Females in whom pregnancy, as recorded in the available data sources, overlaps with ritlecitinib use
- 6. Patients aged <12 years on the index date
- 7. Patients with a serious infection before index date
- 8. Patients with evidence of having measured risk factors and the number of measured risk factors for thromboembolic events within 12 months before index date
- 9. Patients with evidence of having measured risk factors and the number of risk factors for malignancy within 12 months before index date
- 10. Patients with evidence of having measured risk factors and the number of risk factors for CVD within 6 months before index date

The windows for ascertainment of presence of specific events may be revised to reflect the local data flow.

Detailed methodology for summary and statistical analyses of data collected in this study will be documented in a SAP, which will be dated, filed, and maintained by the sponsor. The SAP may modify the plans outlined in the protocol; any major modifications of primary endpoint definitions or their analyses would be reflected in a protocol amendment.

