9.7.1. Sensitivity Analyses

A sensitivity analysis will restrict to the subset of patients with an AA diagnosis on or up to 5 years before the index date.

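### Exposure runs 90 days past estimated discontinuation, so the live-vaccine and pregnancy indicators, which have no other window, would count events after the end of supply as use during treatment

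*Protocol*

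**What the plan says.** Protocol section 9.3.1 fixes the end of exposure: "The exposure will continue until the end of a 90-day grace period following the estimated discontinuation of the index treatment". The stop date is itself an estimate: "Duration of each dispensing will be computed based on days supplied, estimated based on assumed daily dose, package size" and the number of packages. The section adds: "Only the first continuous treatment episode will be considered in this study".

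Two indicators in section 9.7 depend on when a patient counts as treated:

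- Item 4: "Patients with evidence of having received live attenuated vaccines during treatment with ritlecitinib".
- Item 5: "Females in whom pregnancy, as recorded in the available data sources, overlaps with ritlecitinib use".

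Neither item cites section 9.3.1 or gives a window of its own, and section 9.3.1 is the only place where the protocol defines the exposed period.

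The vaccine measure is worded in section 8.2 as "Avoiding live attenuated vaccines shortly before and during treatment with ritlecitinib". The pregnancy measure there, and the summary in section 9.3.2, concern use in pregnancy. None of these names a period after treatment.

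The only sensitivity analysis, in section 9.7.1, concerns the population: "A sensitivity analysis will restrict to the subset of patients with an AA diagnosis on or up to 5 years before the index date". The limitations in section 9.9 do not mention the 90 days, and no reason for that length is given.

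**The concern.** A grace period can do two jobs. It can join dispensings separated by a late refill into one episode, or it can add time after the last supply has run out. Section 9.3.1 does the second: the 90 days follow the estimated discontinuation and belong to exposure.

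A tail of this kind can suit a safety outcome with a carry-over effect. Items 4 and 5 instead measure whether a live vaccine or a pregnancy coincided with treatment. If the section 9.3.1 period is applied to them, a vaccine given or a pregnancy begun after the estimated end of supply enters the count of non-adherence, and the table cannot tell it apart from an event during supply.

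Section 7 says the results will help show whether the risk minimization program has met its objectives or needs amendment. A count that mixes the two kinds of event is a weaker basis for that decision.

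**Working it through.** **The plan's own figure.** Section 9.5 uses n = P(1−P)z²/e². With P = 0.50, z = 1.96 and e = 0.05 (half of a 10-point width), n = 0.25 × 3.8416 / 0.0025 = 384.2, rounded up to 385, as in Table 2. This figure does not depend on the exposure definition. It serves below only as a cohort size, not as a forecast of uptake.

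**Inputs.**

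- Tail: 90 days (section 9.3.1).
- Cohort: 385 patients per database (section 9.5).
- Supplied duration D: not in the document; assumed 90 to 730 days.
- Event rate: not in the document; assumed 1% or 5% per year.
- Estimated discontinuation: taken as the end of supply of the last dispensing.

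**Step 1: share of person-time.** For a patient who discontinues and is followed through the tail, the share of defined exposure after the end of supply is 90/(D+90).

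| Assumed D (days) | Calculation | Share |
|---|---|---|
| 90 | 90/180 | 50% |
| 180 | 90/270 | 33% |
| 365 | 90/455 | 20% |
| 730 | 90/820 | 11% |

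This is a share of time. Section 9.7 reports proportions of patients, so a second step is needed.

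**Step 2: patients flagged.** Assume that all 385 discontinue after D days, are followed through the tail, and have the same constant event rate r before and after the end of supply. The expected number flagged is 385 × [1 − exp(−r × days/365)].

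For D = 180 and r = 5% per year:

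- Without the tail: 385 × [1 − exp(−0.05 × 180/365)] = 385 × 0.0244 = 9.4 patients (2.4%).
- With the tail: 385 × [1 − exp(−0.05 × 270/365)] = 385 × 0.0363 = 14.0 patients (3.6%).
- Difference: 4.6 patients, or 1.2 percentage points. About one third of those flagged (4.6/14.0) would have their event after the end of supply.

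Other assumed values:

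| D (days) | r per year | Without tail | With tail |
|---|---|---|---|
| 90 | 5% | 4.7 | 9.4 |
| 180 | 1% | 1.9 | 2.8 |
| 365 | 5% | 18.8 | 23.3 |

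If the rate in the tail were three times the rate before it, the D = 180, 5% case would go from 9.4 to 23.0. The factor of three is also assumed.

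**Step 3: scale against precision.** At 2.4% with n = 385, the 95% half-width is 1.96 × √(0.024 × 0.976/385) = 1.5 points. The 1.2-point shift in the main illustration is somewhat smaller than that. It is systematic, however, so a larger cohort would not reduce it.

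**The case against.** Several counter-arguments have force.

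- **The link is an inference.** Items 4 and 5 speak of treatment and use, not exposure. Section 9.3.7 leaves refined definitions to the SAP, and section 9.7 lets windows be revised to suit local data. An SAP that is not shown may set a narrower window. This stands. Still, the protocol does state an end-of-exposure rule, and that rule is the only one a reader can apply.
- **Some tail events are on drug.** Supply is estimated from an assumed daily dose, and section 9.9 accepts that pauses may go unseen. Patients who stretch their supply may still be taking the drug. This stands, and it is a reason against a hard stop at the end of supply as the sole definition.
- **Other errors run the opposite way.** Table 1 and section 9.9 say that some vaccines are not recorded (travel and employer-paid vaccines in Denmark, non-reimbursed ones in France). Section 9.9 adds that ongoing and terminated pregnancies are incompletely captured. The net direction of error is therefore not established.
- **Scope is narrow.** Two of ten items are affected, and item 4 cannot be computed in Sweden.

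A reader might also infer that every patient who stops adds 90 drug-free days, that anyone who stops before a vaccine or conception is adherent and wrongly classed as a failure, or that a third to a half of reported events would be false. The documents do not support these readings. The stop date is only estimated, patients still treated when data end have no tail, and the protocol does not say how long after the last dose a vaccine or conception would be acceptable. The percentages in Step 1 are person-time shares under assumed durations.

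**Conclusion.** The point holds in limited form. Followed as written, section 9.3.1 with items 4 and 5 reports events after the estimated end of supply as occurring during treatment or use. The measures as the protocol summarises them do not extend that far, and nothing in the protocol tests or discloses the effect. Taken alone, the tail can only raise these two counts, and proportionately most when episodes are short.

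The size is unknown. The illustrated rise from 2.4% to 3.6% rests on an assumed duration and rate, on every patient discontinuing, and on equal rates before and after the end of supply. The conclusion also rests on reading treatment and use as the exposure of section 9.3.1. Severity is moderate, confined to item 4 in Denmark and France and item 5 in all three countries. The laboratory, age, pre-index infection and risk-factor items and the study size are unaffected.

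**What to change.** State in section 9.3.1 that the 90-day allowance joins consecutive dispensings into one episode. For items 4 and 5 in section 9.7, report:

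- (a) vaccine given, or pregnancy overlapping the period, up to the end of supply of the last dispensing;
- (b) vaccine given, or pregnancy starting, only in the following 90 days;
- the combined count under the current definition.

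Describe only (a) as during treatment or use, and (b) as possible use. This is a reporting split and sets no clinical rule on timing after the last dose.

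The cost is one sentence and one extra table column, using data already held. Extraction is planned from September 2027, so the change can precede any results. There are two downsides. Some patients who stretch their supply will fall in (b). Cells will also be smaller: section 9.10 masks counts of 1 to 4 and any count from which they could be recomputed, so a masked (b) would force masking of (a) or the combined count. In the 1% per year illustration at 180 days, (a) would be about 1.9 and (b) about 0.9, so masking is a real prospect. The table shells should say which count takes priority.

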7. RATIONALE AND BACKGROUND

Alopecia areata (AA) is an autoimmune disease that has an underlying immuno-inflammatory pathogenesis and is characterized by nonscarring hair loss ranging from small patches to complete scalp, face, and/or body hair loss. AA may present as: limited patchy hair loss (patchy alopecia areata), complete loss of hair on the scalp (alopecia totalis [AT]), or complete loss of hair on the scalp and the body (alopecia universalis [AU]). The affected skin usually does not have signs of inflammation.

Both males and females of all ages and races can be affected. AA is the second most common cause of hair loss, affecting approximately 147 million individuals worldwide, with a lifetime risk of all subtypes of approximately 2% (1, 2). Incidence rates of AA range from 20 to 200 per 100,000 person-years [PY(s)], and the global lifetime prevalence worldwide is estimated at 2% (2-8). A meta-analysis including articles published up to 01 September, 2018 estimated the overall pooled incidence proportion of AA in Europe as 4.92% (95% confidence interval [CI] 2.41-8.25%), and the pooled prevalence as 0.58% (95% CI 0.49-0.66%) (9). AA is associated with inflammatory diseases including asthma, allergic rhinitis, atopic dermatitis, and autoimmune diseases such as thyroiditis and vitiligo (10). The natural history and prognosis of AA are unpredictable and can be marked by remission, progression, or persistence (11, 12).

Ritlecitinib was authorized by the European Medicines Agency (EMA), on 15 September 2023, for the treatment of severe alopecia areata in adults and adolescents 12 years of age and older (13). Ritlecitinib is flagged by the Danish authorities as a medication being subject to heightened monitoring (14).

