9.1.1. Study Population and Study Period

The study population will include patients identified in each data source with a record of treatment with ritlecitinib during the study period. The study period will be 5 years following product launch: from 15 September 2023 through 14 September 2028.

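### Live vaccines and pregnancies are to be assessed during ritlecitinib use without limit, but section 9.3.1 lets only the first treatment episode count

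*Protocol*

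**What the plan says.** Protocol section 9.3.1 defines exposure from the first dispensing and closes it as follows: "The exposure will continue until the end of a 90-day grace period following the estimated discontinuation of the index treatment". It then adds: "Only the first continuous treatment episode will be considered in this study".

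The objectives in section 8.2 carry no such limit. Two of them are "Avoiding live attenuated vaccines shortly before and during treatment with ritlecitinib" and "No use during pregnancy". The matching analysis items in section 9.7 are equally open:
- Item 4: "Patients with evidence of having received live attenuated vaccines during treatment with ritlecitinib".
- Item 5: "Females in whom pregnancy, as recorded in the available data sources, overlaps with ritlecitinib use".

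The study period in section 9.1.1 runs "from 15 September 2023 through 14 September 2028". On the disease course, section 7 says: "The natural history and prognosis of AA are unpredictable and can be marked by remission, progression, or persistence".

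Section 9.3.1 gives no reason for the restriction. Section 9.9 does not list it among the limitations. The only sensitivity analysis, in section 9.7.1, restricts to patients with an alopecia areata diagnosis and does not touch the episode rule.

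**The concern.** The question asked and the time at risk that is counted do not match. Someone reading a result for item 4 or 5 would take it to describe all recorded ritlecitinib use in the study period. Under section 9.3.1 it describes the first episode only.

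The patients affected are those who stop for longer than the supply plus 90 days and later restart. They remain among the users on whom the proportion is based. A live vaccine or a pregnancy during the restarted treatment leaves them recorded as having no violation. No planned analysis would show how often this happens, although the study exists to tell the regulator whether these recommendations are followed.

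Items tied to the index date are unaffected: the tests before initiation and at week 4, age, infection before index, and the baseline risk factors. The vaccine part does not arise in Sweden, which has no vaccine data. Table 1 gives a pregnancy definition for all three countries.

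**Working it through.** **The plan's own figure.** The protocol's study-size calculation does not depend on the episode rule, but it supplies a reference size. Section 9.5 uses n = P(1-P)·z²/e². With P = 0.50, e = 0.05 and z = 1.96 this gives 384.15, rounded up to 385, as in Table 2. The other Table 2 entries also reproduce.

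**Direction of the restriction alone.** Every patient with a violation in the first episode also has a violation in at least one episode. The denominator is the same for both counts. So the first-episode proportion cannot exceed the all-episode proportion. This needs no assumption about rates.

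**Possible size.** The protocol gives no restart rate, event rate or episode length, so all three inputs below are assumptions:
- p1, risk of a violation in the first episode: 1% to 5%.
- r, fraction of patients who restart within the study period: 10% to 50%.
- k, risk in the restarted episode relative to p1: 0.5 to 1.0.

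With at most one restart per patient and independent episodes, the proportion with any violation is 1 - (1 - p1)(1 - r·k·p1).

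| p1 | r | k | Any episode | Shortfall (points) | Patients per 385 | Share of violators missed |
|---|---|---|---|---|---|---|
| 1% | 10% | 0.5 | 1.05% | 0.05 | 0.2 | 4.7% |
| 1% | 50% | 1.0 | 1.50% | 0.50 | 1.9 | 33.1% |
| 2% | 30% | 1.0 | 2.59% | 0.59 | 2.3 | 22.7% |
| 5% | 10% | 0.5 | 5.24% | 0.24 | 0.9 | 4.5% |
| 5% | 50% | 1.0 | 7.38% | 2.38 | 9.1 | 32.2% |

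For example, the last row is 1 - 0.95 × 0.975 = 0.07375, against 0.05 in the first episode. Over the whole grid the shortfall runs from 0.05 to 2.4 points, and about 5% to 33% of violating patients are missed. The per-385 column applies to a denominator of 385. Item 5 concerns females only, so its denominator will be smaller than the full cohort.

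**The opposing effect.** The 90-day tail counts time after estimated discontinuation as exposed. For patients who stop, let D be the true length of the first episode and D2 the length of a restarted one, in days. Time counted as treated over time truly treated is (D + 90)/(D + r·D2). The assumed values are D from 90 to 730, with either r = 10-30% and D2 = 180, or r = 30-50% and D2 = 365.
- Highest: D = 90, r = 10%, D2 = 180 gives 180/108 = 1.67.
- Lowest: D = 90, r = 50%, D2 = 365 gives 180/272.5 = 0.66.
- At D = 365 the four combinations give 1.19, 1.09, 0.96 and 0.83.

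The ratio falls on both sides of 1, so the net sign is not determined.

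**The case against.** The strongest defence is that first-episode use among initiators is a coherent quantity, openly stated in section 9.3.1, and that the proportion is correct for it. That stands. The result misleads only if it is read as covering all use, but that is how objective 1 and items 4 and 5 are worded.

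A lost case also needs several steps within the remaining study time: a first course, a gap longer than supply plus 90 days, a restart, and then a violation. Patients enter throughout the five years, so late entrants have little time for this. Shorter gaps stay inside the first episode. Vaccine capture and pregnancy identification are already acknowledged as incomplete. All of this limits the likely size. It does not remove the mismatch.

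Four stronger readings are tempting, and the document does not support them:
- A reader might infer that the protocol describes a relapsing disease in which restarts are expected. Section 7 names remission, progression or persistence as natural history. Relapse and restarting of the drug are plausible inferences, and no rate is given.
- A reader might infer that reported adherence is overstated on balance. The 90-day tail works the other way: a vaccine or pregnancy after the drug has stopped can count as during use. The two errors affect different patients, and nothing makes them cancel, but the net sign is open.
- A reader might equate the undercount with the share of treated time in later episodes. That would be a loss of events. Items 4 and 5 count patients, and someone already counted in the first episode is not lost. The protocol also gives nothing to fix that share.
- A reader might extend the point to serious infection during use. Section 9.7 lists only infection before the index date, so there is no such measure to correct.

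By the same logic, item 3 misses a vaccine given shortly before a restart. Section 9.7 defines that item by the index date, however, so its wording and its window agree.

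**Conclusion.** The point holds for items 4 and 5 of section 9.7. The protocol fixes a rule that discards every later episode, while the objective and the analysis items are worded for all treatment. Neither the limitations nor the sensitivity analysis deals with the difference. For the restriction alone the direction is certain: it can only lower the proportion with a violation relative to all use.

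The size is not known. The range of about 0.05 to 2.4 percentage points, or 0.2 to 9 patients per 385, rests wholly on the assumed risks and restart fractions, with one restart at most and independent episodes. Small numbers still matter here: 1% of 385 is about 4 patients, and section 9.10 masks cells of 1 to 4. No net overstatement of adherence is shown, because the grace period pushes the other way. This is a cheap improvement that lets the study answer its own objective; the first-episode analysis itself is not invalid.

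**What to change.** In sections 9.3.1 and 9.7:
- Keep the first episode for the index-anchored items and the baseline description.
- For items 4 and 5, also count all ritlecitinib episodes in the study period, each built with the same days-supplied rule, and report this beside the first-episode result.
- Give both results with and without the 90-day grace period counted as use, so that the two opposing effects can be seen separately.
- Label the first-episode results as such in the tables.

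In section 9.9, list the restriction as a limitation of any first-episode result.

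The cost is a few sentences, some extra programming to apply the episode algorithm to later dispensings in the same registers, and additional table columns. Data extraction is planned to start in September 2027, so the change can be made before then.
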